#### 2.1.4 **Safety endpoints**

The safety analysis will be based on the reported adverse events (AEs) and other safety information, such as clinical laboratory data and vital signs.

##### ***Observation period***

The observation period of safety data will be as follows:

- **Pre-treatment** period is defined as the time from the signed informed consent date up to the day of randomization.
- **Treatment-emergent adverse event (TEAE)** period is defined as the time from the day of randomization to the last study treatment administration + 21 days, or end of study, whichever comes first in both the alirocumab and SoC groups.

- **Post-treatment** period is defined as the time starting the day after the end of the TEAE period up to the end of the study.
- **On-study observation** period is defined as the time from the day of randomization until the end of the study.

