6.1 DESCRIPTION OF THE STUDY

The study consists of a 36-week open-label treatment period started within 4 weeks after ACS diagnosis and appropriate percutaneous coronary intervention (PCI) with bare metal stent (BMS) or drug eluting stent (DES) placement and includes post-treatment IVUS imaging (evaluation IVUS imaging, Week 36 [end of treatment (EOT)] ± 2 weeks). The patient who did not receive PCI but has undergone coronary artery bypass graft surgery or received medical therapy only can be included if the analyzable IVUS imaging is obtained.

A 36-week open label treatment period: Patients will be randomized to either alirocumab arm or SoC arm. Randomization will be stratified by on statin therapy or not on statin therapy at the ACS onset. While the last Praluent® administration will be performed at Week 34, evaluation IVUS imaging can be carried out between Week 34 and Week 38 (Week 36 ± 2 weeks) considering potential scheduling difficulty. The Investigator/sub-Investigator is to make their best effort to schedule the evaluation IVUS imaging within this time period. If a patient cannot undergo evaluation IVUS by Week 36, the last Praluent® administration will be performed at Week 36 and the Investigator/sub-Investigator will make their best effort to carry out evaluation IVUS before Week 38 while maintaining sufficient alirocumab effect at the evaluation IVUS imaging (see [Section 1.2](#)). Patients in the SoC arm will continue the study treatment until evaluation IVUS.

- Alirocumab arm: Praluent® 75 mg Q2W on top of statin therapy (atorvastatin ≥ 10 mg/day or rosuvastatin ≥ 5 mg/day within the range of statin doses approved by the Health Authority) will be administered.

Note: At Week 14, patients whose LDL-C level measured at Week 12 by central laboratory remains ≥ 100 mg/dL in spite of 75 mg Praluent® administration, will receive Praluent® dose up-titrated to 150 mg Q2W.

Note: Patients can choose self-injection of Praluent® (alirocumab) at home any time, if they wish self-injection at home and the Investigator/sub-Investigator considers it feasible.

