10.4.2 General guidelines for reporting adverse events

All AEs, regardless of seriousness or relationship to study treatment, spanning from the signature of the informed consent form until the end of the study as defined by the protocol for that patient, are to be recorded on the corresponding page(s) or screen(s) of the e-CRF.

Whenever possible, diagnosis or single syndrome should be reported instead of symptoms. The Investigator/sub-Investigator should specify the date of onset, intensity, action taken with respect to study treatment, corrective treatment/therapy given, additional investigations performed, outcome, and his/her opinion as to whether there is a reasonable possibility that the AE was caused by the study treatment or by the study procedure(s).

The Investigator/sub-Investigator should take appropriate measures to follow all AEs until clinical recovery is complete and laboratory results have returned to normal, or until progression has been stabilized, or until death, in order to ensure the safety of the patients. This may imply that observations will continue beyond the last planned visit per protocol, and that additional investigations may be requested by the monitoring team up to as noticed by the Sponsor. When treatment is prematurely discontinued, the patient's observations will continue until the end of the study as defined by the protocol for that patient.

Laboratory and vital signs are recorded as AEs only if:

- Symptomatic and/or
- Requiring either corrective treatment or consultation, and/or
- Leading to study treatment discontinuation or modification of dosing, and/or
- Fulfilling a seriousness criterion, and/or
- Defined as an AESI

See [Section 17](#), Appendix F for summary of AE reporting guidelines.

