11.4.3 Analyses of safety data

The summary of safety results will be presented by treatment arm. No formal inferential testing will be performed. Summaries will be descriptive in nature.

Observation period

The observation period of safety data will be as follows:

- **Pre-treatment period** is defined as the time from the signed informed consent date up to the day of randomization.
- **TEAE period** is defined as the time from the day of randomization up to the last administration + 14 days (+ 7 days), or end of study, whichever comes first.
- **Post-treatment period** is defined as the time starting the day after the end of the TEAE period up to the end of the study (see definition in [Section 6.2.1](#)).
- **On-study observation period** is defined as the time from the day of randomization up to the end of the study (see definition in [Section 6.2.1](#)).

All safety analyses will be performed on the safety population using the following common rules:

- The potentially clinically significant abnormality (PCSA) values are defined as abnormal values considered medically important by the Sponsor according to predefined

criteria/thresholds based on literature review and defined by the Sponsor for clinical laboratory tests and vital signs.

- PCSA criteria will be determined which patients had at least 1 PCSA during the TEAE period, taking into account all evaluations performed during the TEAE period, including unscheduled or repeated evaluations. The number of all such patients will be the numerator for the PCSA percentage.

Drug-induced liver injury

The liver function tests, namely ALT, AST, alkaline phosphatase, and total bilirubin, are used to assess possible drug-induced liver toxicity. The proportion of patients with PCSA values at any post-baseline visit by baseline status will be displayed by treatment arm for each parameter.

A graph of distribution of peak values of ALT versus peak values of total bilirubin will also be presented. Note that the ALT and total bilirubin values are presented on a logarithmic scale. The graph will be divided into 4 quadrants with a vertical line corresponding to $3 \times \text{ULN}$ for ALT and a horizontal line corresponding to $2 \times \text{ULN}$ for total bilirubin.

The incidence of liver-related AEs will be summarized by treatment arm. The selection of preferred terms will be based on standardized MedDRA query (SMQ) "Hepatic disorder."

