#### **2.1.4.2 Deaths**

The deaths observation periods are per the observation periods defined above.

- Death on-study: deaths occurring during the on-study observation period
- Death on-treatment: deaths occurring during the TEAE period
- Death post-study: deaths occurring after the end of the study

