#### **2.4.5.1 Analyses of adverse events**

##### ***Generalities***

The primary focus of AE reporting will be on TEAEs. Pre-treatment and post-treatment AEs will be described separately.

If an AE date/time of onset (occurrence, worsening, or becoming serious) is incomplete, an imputation algorithm will be used to classify the AE as pre-treatment, treatment-emergent, or post-treatment. The algorithm for imputing date/time of onset will be conservative and will classify an AE as treatment-emergent unless there is definitive information to determine it is pre-treatment or post-treatment. Details on classification of AEs with missing or partial onset dates are provided in [Section 2.5.3](#).

AE incidence tables will present, the number (n) and percentage (%) of patients experiencing an AE by SOC, HLTG (when applicable), HLT (when applicable), and PT. Multiple occurrences of the same event in the same patient will be counted only once in the tables within a treatment phase. The denominator for computation of percentages is the safety population within each treatment group.

Sorting within tables ensures the same presentation for the set of all AEs within the observation period (pre-treatment, TEAE, and post-treatment). For that purpose, the table of all TEAEs presented by SOC and PT sorted by the internationally agreed SOC order and decreasing frequency of PTs within SOCs (in the alirocumab group) will define the presentation order for all other tables by SOC and PT, unless otherwise specified. The tables of AEs by SOC, HLTG, HLT and PT will be sorted by the SOC internationally agreed order and the other levels (HLTG, HLT, and PT) will be presented in alphabetical order, unless otherwise specified

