### ***Date of last administration of study treatment***

The date of the last administration is equal to the last date of administration reported on the end-of treatment case report form page, or missing if the last administration date is unknown.

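### The TEAE window closes 21 days after a last-treatment date that is undefined by drug, so alirocumab patients who stop injections but stay in the study may leave the main safety summaries early

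*SAP*

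**What the plan says.** SAP 2.1.4 runs the TEAE period from randomization until 21 days after study treatment was last given, or until end of study, "whichever comes first in both the alirocumab and SoC groups". Protocol 11.4.3 has "up to the last administration + 14 days (+ 7 days), or end of study, whichever comes first". SAP 2.5.1 takes the date from "the last date of administration reported on the end-of treatment case report form page" and names no drug.

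In the control arm, Protocol 6.1 states: "Patients in the SoC arm will continue the study treatment until evaluation IVUS". For a patient in either arm who stops treatment early, Protocol 10.4.2 says that "observations will continue until the end of the study as defined by the protocol for that patient". Protocol 10.3.4 asks such patients to keep the visit schedule to Week 36.

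SAP 2.4.5.1 says: "The primary focus of AE reporting will be on TEAEs". Its percentages use all safety patients in the arm as denominator. Post-treatment AEs and SAEs have separate tables, and adjudicated cardiovascular results are summarized for treatment-emergent events only. SAP 2.1.4 also defines an on-study period, from randomization to end of study. Among the AE, SAE and cardiovascular summaries only deaths use it: "Death on-study: deaths occurring during the on-study observation period".

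**The concern.** If the last injection sets the date, the same wording gives different windows. A control patient who stays on statin is on study treatment until the evaluation IVUS, so nearly everything to study end is treatment-emergent. An alirocumab patient who stops injections but remains under observation is counted for three more weeks only. With patient-count denominators, a shorter window can only lower the displayed incidence in that arm.

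The cardiovascular summary has most at stake. The secondary safety objective (Protocol 5.2, SAP 1.2.2) covers events throughout the study, and Protocol 9.2.1 counts adjudicated events until end of study. Under the SAP, a non-fatal infarction adjudicated more than 21 days after the last injection would appear in no adjudicated summary. The same event in a control patient on statin would be counted.

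Stopping may also come earlier in the alirocumab arm. In Protocol 10.3.3 the compliance criterion for permanent discontinuation applies over 12 weeks for alirocumab and over 6 months for SoC, with an optional 3-month decision for SoC.

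**Working it through.** The documents give no figure for observation time, so there is none to reproduce. The sample size sets the scale: 75 / (1 - 0.25) = 100 randomized per arm.

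**Inputs**
- Window: last administration + 21 days, capped at end of study (SAP 2.1.4).
- Last scheduled injection at Week 34 = Day 239; end of treatment at Week 36 = Day 253 (Protocol 1.2).
- Stopping rate: 4.9% of alirocumab patients had a TEAE leading to permanent IMP discontinuation over 52 weeks in the earlier Japanese phase 3 trial (Protocol 4).
- SAE risk: 12.5% in that trial's placebo group.
- Assumptions: last injection sets the date, stoppers stay to Week 36, and no SoC patient stops.

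**Step 1: one patient.** Close day = min(1 + 7w + 21, 253), where w is the week of the last injection.

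| Last injection | Window closes | Short of Week 36 by |
|---|---|---|
| Week 4 (Day 29) | Day 50, Week 7 | 29 weeks |
| Week 12 (Day 85) | Day 106, Week 15 | 21 weeks |
| Week 24 (Day 169) | Day 190, Week 27 | 9 weeks |
| Week 34 (Day 239) | Day 260, capped at 253 | 0 |

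A completer loses 7 days if the IVUS falls on Day 267 without the Week 36 dose (267 - 260), and 14 days if the last dose was also 7 days early.

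**Step 2: the whole arm.** Fraction lost = f x (36 - (w + 3)) / 36, where f is the proportion stopping.
- f = 0.049, w = 24: 0.049 x 9/36 = 1.2%.
- f = 0.049, w = 8: 0.049 x 25/36 = 3.4%.
- f = 0.049, stops uniform over Weeks 0 to 32 (mean window 16 + 3 = 19 weeks): 0.049 x 17/36 = 2.3%, a mean window of 35.2 against 36 weeks.
- Uniform stops at higher assumed rates: 10% gives 4.7%, 15% gives 7.1%, 25% gives 11.8%. The 25% is an upper illustration, borrowed from the non-evaluable proportion.

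**Step 3: a displayed percentage.** Rescaled to 36 weeks under a constant hazard, the SAE risk is 1 - (1 - 0.125)^(36/52) = 8.8%. With uniform stops it would show as 8.6% at 4.9% stopping, about 0.2 of a patient in 100. At 25% stopping it would show as 7.8%, about one patient.

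**Step 4: the other reading.** If a continuing statin sets the date, both windows run to Week 36. The same date, however, enters the as-treated formula in SAP 2.3.2. A patient with 9 injections, the last at Week 16, then scores 9 / (252/14 + 1) = 9/19 = 47.4%. That is below 50%, so the patient is analyzed as SoC. On the injection reading the score is 9 / (112/14 + 1) = 100%. Protocol 11.3.2 uses the end-of-treatment date in this place.

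**Step 5: where events after the window go.**

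| Event | Planned summary |
|---|---|
| AE or SAE | Separate post-treatment tables (SAP 2.4.5.1) |
| AESI grouping | None; groupings are built from TEAEs |
| Non-fatal adjudicated cardiovascular event | No adjudicated summary; the AE itself is in the post-treatment tables |
| Death | On-study, with adjudicated cause (SAP 2.4.5.2) |

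**The case against.** The strongest reply is that the documents never say the injection sets the date. Where the SAP means injections it says so, as in the exposure definition in 2.4.3.1, and 2.3.2 uses both terms within one formula. The protocol synopsis describes the alirocumab regimen as combination therapy that includes statin. This stands: the injection reading is an inference. It remains the more natural one, because Protocol 10.3.2 defines permanent discontinuation by the IMP, SAP 2.3.2 names the study drug as alirocumab or standard of care, and the protocol's 14 days equals the dosing interval. Step 4 shows that the statin reading has its own consequence.

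A second reply is that an exposure-tied window is deliberate, safety is descriptive with no test affected, and late events are tabulated. The SAP also plans AEs per patient-months in three intervals. These points limit the concern without removing it. The patient-months table stays within the TEAE period and has no stated SAE or cardiovascular version, and the post-treatment tables carry no AESI groupings or adjudicated results.

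Third, SoC patients who stop study treatment are cut by the same rule, and patients who leave the study when they stop are closed by study end in either arm. Both points stand.

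A reader might also infer that the event that caused a patient to stop is lost. It is not: it began before the window closed and is a TEAE.

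**Conclusion.** The point holds in limited form. The date that closes the TEAE window is not defined by drug in the alirocumab arm. On the more natural reading, early stoppers who remain in the study are observed for less time in the main tables than SoC patients who continue statin. Late non-fatal adjudicated cardiovascular events then fall outside every adjudicated summary, against an objective that covers the whole study.

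The size is about 1% to 3% of alirocumab observation time at the 4.9% rate. That rate counts AE-related stops only, so all-cause stopping could be higher. The estimate also assumes that stoppers stay to Week 36 and that no SoC patient stops.

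A reader might go further and conclude that the arms are followed unequally in general, or that a tenth of the observation time is lost. The documents do not support either. Completers have practically equal windows. A loss near 10% needs, for example, 15% stopping after Week 8 (0.15 x 25/36 = 10.4%), and no passage gives such a rate. No hypothesis test or alpha is affected, so this is a worthwhile low-cost improvement.

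**What to change.** 1. In SAP 2.1.4 and 2.5.1, state for each arm which administration sets the last study treatment date.
2. Use that date consistently in the as-treated formula in SAP 2.3.2, and reconcile it with the end-of-treatment date in Protocol 11.3.2.
3. Keep the TEAE tables. Add overview, SAE, AESI and adjudicated cardiovascular tables for both arms over the on-study period already defined in SAP 2.1.4.

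The cost is a few tables from data already collected. The drawback is that off-drug events enter the on-study tables, which is why the TEAE tables should stay beside them. Follow-up will be equal as planned but not identical, because Protocol 6.2.1 extends a patient's end of study until SAEs and AESIs resolve or stabilize; a footnote can say so.

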#### **2.1.4.1 Adverse events variables**

Occurrence of adverse events (including SAEs and adverse events of special interest [AESIs]) are recorded from the time of signed informed consent until the end of study.

All AEs (including SAEs and AESIs) will be coded to a lowest-level term (LLT), PT, high-level term (HLT), high-level group term (HLGT), and associated primary system organ class (SOC) using the version of MedDRA currently in effect at Sanofi or delegate at the time of database lock.

#### ***Adverse event observation period***

- Pre-treatment AEs are AEs that developed or worsened or became serious during the pre-treatment period
- TEAEs are AEs that developed or worsened or became serious during the TEAE period
- Post-treatment AEs are AEs that developed or worsened or became serious during the post-treatment period

#### ***Adverse events of special interest***

Adverse events of special interest (AESIs) are adverse events (serious or non-serious) that need to be monitored, documented, and managed in a pre-specified manner described in the protocol. In this study, AESIs are the following (their complete descriptions are provided in the protocol):

- General allergic events, selected using SMQ “hypersensitivity” (broad and narrow) excluding the following preferred terms linked to local injection site reactions (“infusion site dermatitis”, “infusion site hypersensitivity”, “infusion site rash”, “infusion site urticaria”, “injection site dermatitis”, “injection site hypersensitivity”, “injection site rash”, “injection site urticaria”, and “injection site vasculitis”)
- General allergic events and local allergic reactions at IMP injection site, selected based on the above selection for general allergic event and on the following selection of PT from the symptoms complementary form for local injection site reaction (“Injection site dermatitis”, “Injection site hypersensitivity”, “Injection site oedema”, “Injection site rash”, “Injection site urticaria”, “Injection site eczema”, “Injection site vasculitis”, “Injection site swelling”, “Infusion site dermatitis”, “Infusion site hypersensitivity”, “Infusion site oedema”, “Infusion site rash”, “Infusion site urticaria”, “Infusion site swelling”).
- Local injection site reactions, selected using e-CRF specific tick box on the adverse event page
- ALT >3 ULN, selected using laboratory data

- Hemolytic anemia, selected using e-CRF specific tick box on the adverse event page and confirmed final diagnosis provided in the adverse event complementary form
- Neurologic events selected using a CMQ, based on SMQs “demyelination” (broad and narrow), “peripheral neuropathy” (broad and narrow), and “Guillain-Barre syndrome” (broad and narrow) excluding the following preferred terms “acute respiratory distress syndrome”, “asthenia”, “respiratory arrest” and “respiratory failure”
- Neurocognitive events selected using a CMQ, based on the following 5 HLGTs: “deliria (including confusion)”, “cognitive and attention disorders and disturbances”, “dementia and amnestic conditions”, “disturbances in thinking and perception”, and “mental impairment disorders”
- Ophthalmologic events selected using SMQs “optic nerve disorders” (broad and narrow), “retinal disorders” (narrow), and “corneal disorders” (narrow);
- Skeletal muscle-related adverse events using a CMQ based on the following PTs ”Myalgia”, ”Muscle contractions involuntary”, ”Muscle spasms”, ”Muscle twitching”, ”Muscle fatigue”, ”Muscle tightness”, ”Myofascial spasm”, ”Muscular weakness”, ”Limb discomfort”, ”Musculoskeletal discomfort”, ”Musculoskeletal pain”, ”Pain in extremity”, ”Back pain”, ”Muscle contracture”, ”Musculoskeletal stiffness”
- Overdose of Investigational Medical Product (IMP) (symptomatic), selected using the preferred terms "Accidental overdose" and "Intentional overdose" and the tick box "Overdose with IMP" and "Symptomatic Overdose" in the adverse event complementary e-CRF form
- Pregnancy (including partner of a randomized male subject) selected using appropriate MedDRA codes

The additional grouping of events will be also provided:

- Hepatic disorder events using SMQ “Hepatic disorder”
- Diabetes mellitus or diabetic complications using HLT “diabetes complications” (including PTs pertaining to the secondary SOC included in the HLT), HLT “diabetes mellitus”, and HLT “carbohydrate tolerance analyses (incl diabetes)” excluding PTs “blood glucose decreased” and “Glycosylated haemoglobin decreased” and including the PTs “hyperglycaemia”, “Hyperglycaemic unconsciousness” and “Hyperglycaemic seizure” from the HLT “Hyperglycaemic conditions NEC”
- Cataract using HLT “Cataract conditions”

### ***Cardiovascular events***

Suspected CV events that occur from randomization until the follow up visit will be submitted to the Clinical Events Committee (CEC) for adjudication.

Adjudicated CV events include all CV AEs and CV procedures positively adjudicated as defined in the CEC charter. The following categories will be described:

- CV death (including undetermined cause),
- MI,
- Ischemic stroke,
- Unstable angina requiring hospitalization,
- Congestive heart failure requiring hospitalization,
- Ischemia driven coronary revascularization procedure.

#### **2.1.4.2 Deaths**

The deaths observation periods are per the observation periods defined above.

- Death on-study: deaths occurring during the on-study observation period
- Death on-treatment: deaths occurring during the TEAE period
- Death post-study: deaths occurring after the end of the study

